3.3.1 Main diagnosis for study entry

Patients between 0 to less than 18 years of age with a confirmed acute venous thromboembolism diagnosis and an anticipated requirement for at least 3 months of anti-thrombotic treatment; patient screening may start as soon as the patient has been diagnosed with a VTE. It is expected that parenteral therapy would be administered for a minimum of 5

Proprietary confidential information.

© 2019 Boehringer Ingelheim International GmbH or one or more of its affiliated companies. All rights reserved.

This document may not - in full or in part - be passed on, reproduced, published or otherwise used without prior written permission.

to 7 days using an unfractionated heparin (UFH) or a low molecular weight heparin (LMWH) in all study participants, although for some patients a longer period of initial therapy may be given (but not exceeding 21 days).

3.3.2 Inclusion criteria

- 1) Male or female subjects 0 to less than 18 years of age at the time of informed consent / assent.
- 2) Documented diagnosis of clinically stable VTE (e.g. DVT, PE, central line thrombosis, sinus vein thrombosis) per investigator judgment, initially treated (minimum of 5 to 7 days, but not longer than 21 days) with parenteral anticoagulation therapy, such as unfractionated heparin (UFH) or a low molecular weight heparin (LMWH)².
- 3) Anticipated treatment duration with anticoagulants for the VTE episode (under inclusion 2) for at least 3 month period, inclusive of the initial parenteral therapy.
- 4) Written informed consent provided by the patient's parent or legal guardian and assent provided by the patient (if applicable) at the time of ICF signature according to local regulations.

3.3.3 Exclusion criteria

- 1) Conditions associated with an increased risk of bleeding:
 - a) Any prior intracranial haemorrhage, classified as a macrobleed¹. Any intracranial anatomical abnormality or intracranial aneurysm. Active meningitis, encephalitis, or intracranial abscess at randomisation.
 - b) Intracranial or intraspinal surgeries within 6 months of Visit 2 or any other major surgery within 4 weeks of Visit 2. Major surgeries may include an invasive operation upon an organ within the cranium, chest, abdomen, pelvic cavity or any other procedure regarded as major surgery per investigator judgment. In general, in major surgery, a mesenchymal barrier is opened (pleural cavity, peritoneum, meninges). Removal or insertion of a central venous line is not considered a major surgery provided haemostasis is achieved after the procedure.
 - c) Any major planned procedure that might put the patient at an increased risk of a bleed per investigator judgment within 5 days prior to taking study medication.
 - d) History of intraocular, spinal, retroperitoneal or atraumatic intra-articular bleeding unless the causative factor has been permanently treated (e.g. by surgery).
 - e) Gastrointestinal haemorrhage within the past year prior to screening unless the cause has been permanently eliminated (e.g., by surgery).
 - f) History of gastroduodenal ulcer disease.

¹ Patients with asymptomatic petechial or microbleeds may be included into the study as per investigator's judgment. As a general recommendation, an intracranial microbleed is considered to be ≤ 0.5 cm in greatest diameter on gradient recalled echo (GRE), or T2* MRI sequences (criteria may vary depending on MRI

imaging modalities; [R15-2999](#)). Irrespective of size, any cerebral bleed that causes focal neurologic symptoms and/or signs does not constitute a microbleed. Further, any blood visualized on a CT should be classified as a macrobleed, which is an exclusion criterion for the trial.

² Short-term pre-treatment with VKAs is permitted if the INR has not yet reached a therapeutic level (i.e. the INR is still < 2.0). The duration of the initial parenteral therapy inclusive VKA treatment if applicable must not exceed 21 days.

- g) History of haemorrhagic disorder or bleeding diathesis (e.g. von Willebrand disease, haemophilia A or B or other hereditary bleeding disorder, history of spontaneous intra-articular bleeding, history of prolonged bleeding after surgery/intervention).
 - h) Fibrinolytic agents within 48 hours of dabigatran administration (use of tissue plasminogen activators (t-PA), e.g. alteplase, or any other thrombolytic agents to re-establish patency of obstructed central venous line are allowed as long as the used dose is devoid of relevant systemic effects).
 - i) Uncontrolled hypertension on antihypertensive medication (systolic and/or diastolic blood pressure (BP) above the upper limit of normal for age and sustained over 24 hours).
 - j) Any other disease, health condition or intervention which in the investigator's opinion exposes the patient to a higher risk for bleeding.
- 2) Renal dysfunction (eGFR < 50 mL/min/1.73m² using the Schwartz formula, refer to [Appendix 10.1](#)) or requirement for dialysis. eGFR retesting during the screening period is allowed (once).
- 3) Active infective endocarditis.
- 4) Subjects with a heart valve prosthesis requiring anticoagulation.
- 5) Hepatic disease:
- a) Active liver disease, including known active hepatitis A, B or C or,
 - b) Persistent alanine aminotransferase (ALT) or aspartate transaminase (AST) or alkaline phosphatase (AP) > 3x upper limit of normal (ULN) within 3 months of screening. Transient increases of these parameters are acceptable, if retesting demonstrates results within these limits.
- 6) Pregnant or breast feeding females. Females who have reached menarche and are not using a medically accepted contraceptive method per local guidelines. Acceptable methods of birth control are listed below and must be used in a correct and consistent manner:
- i) Oral or parenteral (patch, injection, implant) hormonal contraception which has been used continuously for at least one (1) month prior to the first dose of study medication
 - ii) Intrauterine device (IUD) or intrauterine system (IUS)
 - iii) Double-Barrier method of contraception: condom and spermicidal agent

Proprietary confidential information.

© 2019 Boehringer Ingelheim International GmbH or one or more of its affiliated companies. All rights reserved.

This document may not - in full or in part - be passed on, reproduced, published or otherwise used without prior written permission.

- iv) Complete sexual abstinence. Note: Periodic abstinence (e.g., calendar, ovulation, symptothermal, post-ovulation methods) and withdrawal are not acceptable methods of contraception.
- 7) Patients in stratum 3 (0 to < 2 years) with gestational age at birth < 37 weeks or with body weight lower than the 3rd percentile (according to the WHO Child growth standards - will be provided in the ISF).
- 8) Anaemia (haemoglobin < 80g/L) or thrombocytopenia (platelet count < 80×10^9 /L) at screening. Transfusions during the screening period are allowed, provided that a satisfactory haemoglobin or platelet level is attained prior to Visit 2.
- 9) Patients who have taken prohibited or restricted medication within one week of the first dose of study medication other than medication for prior VTE treatment and P-glycoprotein inhibitors. For trial restrictions please see [Section 4.2.2](#).
- 10) Patients who have received an investigational drug in the past 30 days prior to screening.
- 11) Patients who are allergic/sensitive to any component of the study medication including solvent.
- 12) Patients or parents/legal guardians considered unreliable to participate in the trial per investigator judgment or any condition which would present a safety hazard to the patient based on investigator judgment.
- 13) Patients or parents/legal guardians who are unwilling or unable to undergo or permit repeat of the baseline imaging tests required to confirm thrombus resolution at study day 84 (or at eEOT, whichever comes first) or in whom repeating such imaging tests at these pre-specified time points may not be medically in the patient's best interest. Examples may include unwarranted radiation exposure as a result of a repeat CT scan at study day 84 (or eEOT, whichever comes first) for a patient with an isolated case of pulmonary embolism evaluated at baseline solely by a CT scan. In such cases, the baseline radiological assessment (e.g. CT) may be supplemented with an acceptable non-radiological assessment at baseline (e.g. MRI) which could then be repeated at day 84 (or eEOT, whichever comes first) hence alleviating any potential unwarranted radiation exposure.

3.3.4 Removal of patients from therapy or assessments

3.3.4.1 Removal of individual patients

The parent(s) / legal guardian(s) and/or their child may decide to be removed from the study as follows:

- The patient/parent/legal guardian may decide to discontinue from treatment and wish to switch to another treatment prior to end of trial and be willing to be followed up within the clinical trial until the time at which study completion would have occurred.

Proprietary confidential information.

© 2019 Boehringer Ingelheim International GmbH or one or more of its affiliated companies. All rights reserved.

This document may not - in full or in part - be passed on, reproduced, published or otherwise used without prior written permission.

- The patient/parent/legal guardian may decide to discontinue study treatment or not participate in any further trial related activities, but be willing to be contacted once at a time point at which the patient would have completed the study to determine the patient's vital status.
- In very rare cases, the patient/parent/legal guardian may withdraw consent/assent to continue in the study for any reason; in doing so they refuse to participate in any further trial related activities and decline any contact or data to be collected for trial purposes. If this occurs, this decision must be clearly documented.

An individual patient is to be discontinued from trial treatment, but will remain part of the analysis population:

- If the patient is no longer able to participate for other medical reasons (e.g. surgery, AEs, other diseases or concomitant therapies).
- In the event that a new thromboembolic event or a clear clinical progression of the baseline VTE (e.g. based on ISTH guidelines) are observed as assessed by the Investigator and using appropriate imaging modalities or if the patient experiences a drug-related significant or drug-related serious AE or if drug toxicity is observed, then the patient is to be removed from the dabigatran treatment arm and be put on standard of care per investigator judgment and be followed until the end of the study. Subjects in the SOC arm may also require changes in their therapy.
- Patients who do not reach a total dabigatran plasma trough concentration within the pre-specified therapeutic range after one dose adjustment.
- In the opinion of the Investigator, continuation in the trial is not in the patient's best interest. If treatment non-compliance persists despite all possible efforts, patients should be removed from the allocated treatment and alternative therapy should be proposed in such cases.
- If a patient becomes pregnant or a pregnancy is suspected during the trial the investigational drug (dabigatran) will be stopped, the patient will be discontinued from the dabigatran treatment arm and will be put on an appropriate SOC therapy per investigator judgment. The patient will be followed up until the end of the study and until the birth or otherwise termination of the pregnancy. For further information, including the process for follow-up on the outcome of the pregnancy, please see [Section 5.2.2.2](#).
- If a patient develops an active meningitis, encephalitis, or intracranial abscess.
- If a patient develops renal dysfunction anytime during the course of the study (eGFR < 50 mL/min/1.73m² using the Schwartz formula, confirmed by one retesting within 14 calendar days), treatment with dabigatran must be stopped and the patient must be switched to an appropriate SOC regimen.
If a patient develops eGFR < 50 mL/min/1.73m² using the Schwartz formula for

Proprietary confidential information.

© 2019 Boehringer Ingelheim International GmbH or one or more of its affiliated companies. All rights reserved.

This document may not - in full or in part - be passed on, reproduced, published or otherwise used without prior written permission.

second time during the course of the study, treatment with dabigatran etexilate (when applicable) must be stopped without further retesting and the patient must be switched to an appropriate SOC regimen.

- The patient does not require treatment with anticoagulants any longer due to a complete thrombus resolution as confirmed by appropriate imaging modalities prior to 12 weeks of planned anticoagulation treatment. In such cases, an early EOT visit is to be performed and the patient should still be followed up according to the remaining visit schedule until the end of the study.

A patient can be discontinued from treatment after discussion between patient/parent/legal guardian, sponsor and Investigator if eligibility criteria are being violated, or if the patient and/or parent/legal guardian fail to comply with the protocol (e.g. non-attendance at trial assessments, improper drug intake, etc.). In such cases and when feasible, the patient is to be followed until the end of study preferably according to the remaining visit schedule.

In addition, in order to protect patient safety, measurements of dabigatran trough plasma levels will be performed in a central laboratory using HPLC-MS/MS or dTT assay or an alternative assay from blood samples taken at steady state (initially after a minimum of three to five days on study treatment, i.e. at minimum after six consecutive dabigatran doses are taken). If a patient has a dabigatran plasma level of $< 50\text{ng/mL}$ or $\geq 250\text{ng/mL}$ confirmed despite a dose adjustment, they will stop taking dabigatran and will be switched to SOC for the remainder of the study.

Dabigatran is predominantly excreted by the kidney; special attention should be given to the kidney function of these patients when needed. As stated above, patients with an $\text{eGFR} < 50 \text{ mL/min/1.73m}^2$ using the Schwartz formula at the screening visit (Visit 1) or any patient with confirmed $\text{eGFR} < 50 \text{ mL/min/1.73m}^2$ at any time during the treatment period will be excluded from the dabigatran arm and will be switched to SOC for the remainder of the study. Any suspected worsening of renal function during the study should be investigated by eGFR evaluation.

Patients who drop out during screening (i.e. prior to randomisation at Visit 2) will be considered a screening failure. These cases have to be recorded as a screening failure in the electronic case report form (eCRF) and no further follow-up is required.

Patients who discontinue study drug or withdraw from the trial after randomisation (Visit 2) will be considered as “early discontinuations” and the reason for premature discontinuation must be recorded in the eCRF. The data will be included in the trial database and will be reported.

All patients that prematurely discontinue dabigatran for various reasons as outlined above and who do not withdraw consent/assent will be switched to SOC after a dabigatran eEOT visit and then followed for the remainder of the study preferably according to the remaining visit schedule. In cases where the patient/parent/legal guardian does not allow for a follow-up according to the remaining schedule and where consent/assent is not withdrawn, the patient/parent/legal guardian will be contacted by the Investigator to perform a dabigatran

Proprietary confidential information.

© 2019 Boehringer Ingelheim International GmbH or one or more of its affiliated companies. All rights reserved.

This document may not - in full or in part - be passed on, reproduced, published or otherwise used without prior written permission.

eEOT visit (i.e. before 12 weeks of treatment) and subsequently be contacted at 4 months in order to gather information for study endpoints (e.g. bleeding events, survival, occurrence of VTE, etc.). If an outcome event is reported to the site (e.g. bleeding events, occurrence of VTE, etc.) then, to ensure patient safety, the patient/parent/legal guardian will be asked to come to clinic for an unplanned visit as soon as possible.

Procedures to be followed for patients prematurely terminating the trial are detailed in [Section 6.2.3](#).

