- D. Unscheduled clinic visits are to be conducted in all cases of suspected symptomatic and asymptomatic VTE, progression/recurrence of VTE, paradoxical embolism (PDE), occurrence of post-thrombotic syndrome (PTS), major or clinically relevant bleeding events (MBEs / CRBEs) or other suspected significant AE or SAE. The unscheduled visit should be performed as soon as possible, preferably within 24 hours after the site first becomes aware of a suspected event. This visit should include all appropriate diagnostic procedures. If VTE progression/recurrence, PDE, PTS, MBEs, CRBEs are confirmed, the patient taking dabigatran etexilate is to be discontinued from the dabigatran etexilate treatment arm (eEOT visit to be performed as soon as possible), and an appropriate standard of care VTE treatment should be initiated per the investigator's discretion and/or local guidelines and the patient should be followed for the remainder of the study. If it is decided that a patient is to be discontinued from treatment due to an event, an eEOT visit should be conducted.
An unscheduled Visit is also to be performed in case a dabigatran etexilate dose adjustment is needed.
- E. The early End Of Treatment (eEOT) visit will be required for all patients who have taken a dose of dabigatran etexilate but failed to complete the full planned treatment observation period (completion of Visit 8). If feasible, this visit is also required for patients randomized to SOC should they decide to discontinue the trial or permanently stop SOC treatment for any reason. eEOT visit is not required if the SOC treatment is changed during the course of the trial.
- F. The informed consent (and if applicable assent) should be obtained per local legislations and guidelines from the patient's parent(s) or legal guardian and patient where applicable before any study procedures are performed. Should patients reach legal age during the trial they must personally sign and date the informed consent form as soon as possible and, at the latest, at the next visit
- G. Prior to start of therapy, all study inclusion and exclusion criteria must be checked to confirm patient eligibility.

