6.2.3 End of trial and follow-up period

Patients who complete the treatment period and are not enrolled into the secondary VTE prevention study (BI trial 1160.108) are to be followed at Visit 9. For the schedule of assessments and procedures to be done at the follow-up visit refer to the [Flow Chart](#).

All patients who prematurely discontinue study medication will be invited to perform an eEOT Visit and the follow-up Visit 9, taking place 28 days thereafter. Subsequently they will be followed-up preferably according to the remaining visit schedule until the end of the

Proprietary confidential information.

© 2019 Boehringer Ingelheim International GmbH or one or more of its affiliated companies. All rights reserved.

This document may not - in full or in part - be passed on, reproduced, published or otherwise used without prior written permission.

study. At these visits collection of AEs, outcome events (e.g. occurrence of PTS, VTE, bleeding events, etc.) and use of concomitant medication will be done.

Patients having switched from dabigatran etexilate to SOC are considered as having early discontinuation of dabigatran etexilate treatment. However, such patients will still remain in the trial and will be followed as per the visit schedule till the end of the study. Patients having switched from one SOC to another during the treatment period, are not considered as having early discontinuation of treatment and should remain in the treatment period and be followed as per the visit schedule till the end of the study.

Proprietary confidential information.

© 2019 Boehringer Ingelheim International GmbH or one or more of its affiliated companies. All rights reserved.

This document may not - in full or in part - be passed on, reproduced, published or otherwise used without prior written permission.

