The presence of recurrent VTE(s) will be examined throughout the study periods. Unscheduled visits would be conducted in case of suspected recurrence of VTE, so the risk of failure to detect recurrent VTE would be minimized. Patients with multiple recurrent VTEs will be regarded equally as patients with a single recurrent VTE, and only the date of first occurrence will be used for analysis.

Proprietary confidential information © 2019 Boehringer Ingelheim International GmbH or one or more of its affiliated companies

- For patients with recurrent VTE(s) from randomization to Day 84 + 7 days, the component of “free from recurrent VTE” will be considered as NOT satisfied.
- For patients WITHOUT ANY recurrent VTE records:
 - If the entire treatment period is completed (Visit 8 available), the component of “free from recurrent VTE” will be considered as satisfied.
 - If patients die (not VTE-related) or withdraw consent prior to Day 84 - 7 days, the period for VTE assessment ends with the date of trial termination (i.e. the date of death, or the date of consent withdrawal). In the primary analysis, we use last-observation-carried-forward (LOCF)², so no record of recurrent VTE will be considered as “free from recurrent VTE”.
 - If patients discontinue treatment prematurely due to reasons other than death or consent withdrawal, they are expected to be followed up for the remainder of planned study visits and will remain in the randomized set. The decision of whether achieving this efficacy endpoint component depends on the timing of their last study visit, if
 - Last study visit¹ took place on or after Day 84 + 7 days and there is no record of recurrent VTE ever, then the component of “free from recurrent VTE” will be considered as satisfied;
 - Last study visit took place before Day 84 + 7 days, then this component will be considered as missing. In the primary analysis, we use last-observation-carried-forward (LOCF)², so no record of recurrent VTE will be considered as “free from recurrent VTE”.
- Patients with VTE recurrence after Day 84 + 7 days will be considered as recurrent VTE free in the primary analysis,

1. Early discontinued patients should be followed up based on IIT principle, so the last study visit could be Visit 9 or further follow-up visit which is available and latest in time.

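### For families who decline further visits, the 4-month contact about VTE and bleeding is written only for dabigatran stoppers; a standard-of-care child who declines every further visit has only a vital-status contact

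*Protocol*

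**What the plan says.** Protocol section 3.3.4.1 lists what a family may choose. The second option is to stop treatment or trial activities but be "contacted once at a time point at which the patient would have completed the study to determine the patient's vital status". It names no arm. Full withdrawal of consent is a separate, third option.

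Later in the same section a second rule begins: "All patients that prematurely discontinue dabigatran for various reasons as outlined above". Where the family "does not allow for a follow-up according to the remaining schedule and where consent/assent is not withdrawn", the site is to obtain a dabigatran eEOT visit, and the family will "subsequently be contacted at 4 months in order to gather information for study endpoints (e.g. bleeding events, survival, occurrence of VTE, etc". No matching contact is written for children who stop SOC.

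Other places apply to both arms:

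- Protocol 6.2.3: "All patients who prematurely discontinue study medication will be invited to perform an eEOT Visit and the follow-up Visit 9", then preferably the remaining visits. "At these visits collection of AEs, outcome events (e.g. occurrence of PTS, VTE, bleeding events, etc" is done there.
- Flow Chart footnote E, on the eEOT visit: "If feasible, this visit is also required for patients randomized to SOC should they decide to discontinue the trial or permanently stop SOC treatment".
- Flow Chart footnote D calls for an unscheduled visit whenever a recurrence is suspected.
- Section 3.3.4.1 also asks, where feasible, that children taken off treatment for non-compliance be followed to the end of the study.
- Protocol 7.3 and 7.4 and SAP 6.6 commit in general terms to following patients who stop early.

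For the recurrence component, SAP 7.4 carries the last observation forward when the last visit falls before Day 84 + 7, "so no record of recurrent VTE will be considered as" free from recurrence. Its footnote justifies this by the low risk, under the study design, of failing to detect one.

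**The concern.** Two children in the same position could be asked different things because of their arm. Each has stopped study medication, declines further visits and has not withdrawn consent. For the dabigatran child the site has a written duty to ask about VTE. For the SOC child the only contact specified establishes whether the child is alive.

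A recurrence that nobody asks about becomes a recurrence-free record under the SAP. Blinded adjudication cannot recover an event that was never reported. Treatment is open-label, so ascertainment rules should be visibly identical by arm. At stake are the recurrence component of the primary composite and freedom from recurrent VTE, which SAP 5.2.2 and 7.5.2 also analyse as a separate proportion.

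**Working it through.** **Step 1: the follow-up rules by situation.**

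- *Accepts visits:* outcomes are collected in both arms (Protocol 6.2.3). No gap.
- *Changes from one SOC to another:* not a discontinuation, and the child stays on schedule (Protocol 4.1.4 and 6.2.3). No gap.
- *Withdraws consent:* no contact in either arm. No gap.
- *Stops, declines every further visit, keeps consent:* an endpoint contact at 4 months is specified for dabigatran and only a vital-status contact for SOC. Section 6.2.3 gives no fallback for refused visits, footnote E is conditional on feasibility, and the general statements do not say how this child is to be followed. This is the gap.

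**Step 2: the plan's own power figure.** Using the protocol's bound (unpooled standard error, z = 1.64, 94 and 47 patients, margin 20 points) in 400,000 simulations, 72% success in both arms gives 81.8%, against 82% stated. The other rows of Table 7.6: 2 come out at 95.2%, 63.3%, 32.3% and 4.7%, against 95%, 63%, 33% and 5%. The stated power stands.

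**Step 3: size of the gap.** Inflation of SOC success = d × f × r × c, where

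- d = share of SOC children who stop. Assumed 15%, about 7 of 47 (47 × 0.15 = 7.05). Protocol 7.6 gives up to 15% for dabigatran only.
- f = share of stoppers who refuse every further visit. Not in the documents; assumed 10% to 50%, with 100% as the extreme.
- r = recurrence, 5.6% to 10.0%. These are the earlier paediatric trial's rates of recurrent VTE or death (Protocol 1.1), used as a stand-in.
- c = share with documented resolution before leaving. Assumed 72% to 100%.

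Results:

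- Low: 0.15 × 0.10 × 0.056 × 0.72 = 0.0006, or 0.06 points (0.03 of a patient among 47). Power 81.7%.
- Middle: 0.15 × 0.25 × 0.10 × 0.72 = 0.0027, or 0.27 points (0.13 of a patient). Power 81.0%.
- High: 0.15 × 0.50 × 0.10 × 1.0 = 0.0075, or 0.75 points (0.35 of a patient). Power 79.4%.
- Extreme, every stopper refuses: 0.15 × 1.0 × 0.10 × 1.0 = 0.015, or 1.5 points (0.7 of a patient). Power 77%.

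Power was simulated with the apparent SOC rate raised by the inflation and dabigatran held at 72%.

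**Step 4: why these figures lean high.** The rates r include deaths. Protocol 1.1 reports five deaths in that trial, all considered unrelated to VTE, and a vital-status call would record a death. The rates also cover a whole follow-up period, whereas only recurrences after leaving can be missed, and Protocol 2.3 places the highest thrombotic risk in the first 30 days. For c, the Flow Chart schedules imaging only at screening, Visit 8 and eEOT. A SOC child who also declines the eEOT visit, and has no unscheduled image, already fails the resolution component under SAP 7.4.

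**The case against.** A reader might infer that recurrences after leaving are sought in the dabigatran arm and not in the SOC arm. The documents do not support that. Sections 3.3.4.1, 6.2.3, 7.3 and 7.4, Flow Chart footnotes D and E and SAP 6.6 provide or invite follow-up in both arms. The vital-status option is also open to dabigatran families.

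A reader might also infer that the two rules contradict each other. They can be read as tiers: one describes what a family may agree to, the other what the site does when a family will still take an eEOT visit and a call. The dabigatran wording has an understandable origin too, since the paragraph deals with switching from dabigatran to SOC. This removes the charge of flat contradiction, but the site's duty to ask about endpoints is still written for one arm.

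Nor is it certain that a dabigatran leaver's recurrence would be counted. The primary analysis uses adjudicated events up to Day 84 + 7, so a 4-month contact must yield a dated event that can be adjudicated. That objection stands, and it is a reason to ask for dates.

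Finally, missed SOC events favour SOC, so this gap cannot create a false claim of non-inferiority. That also stands. It does not make the gap harmless: the estimate, the superiority test and the separate recurrence comparison would still depend partly on who was asked.

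**Conclusion.** The concern holds in a narrow form. For a SOC child who stops, declines every further visit and keeps consent, no endpoint contact is specified, while the dabigatran counterpart has one. The SAP then records the unasked child as recurrence-free.

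The likely inflation of SOC success is 0.06 to 0.75 points, with 1.5 as an extreme, and power falls from about 82% to between 81.7% and 79.4% (77% in the extreme). These figures rest on assumed SOC stopping and refusal rates and on recurrence-or-death rates used for recurrence, and they probably overstate the effect. The direction is against dabigatran.

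In the composite, a missed recurrence matters only after documented resolution. In the separate analysis of freedom from recurrent VTE that filter does not apply. Major bleeding is less exposed, because its analysis window closes six days after the last dose.

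**What to change.** In Protocol section 3.3.4.1, make two wording changes.

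1. In the paragraph containing the 4-month contact, replace the restriction to dabigatran with study medication in either arm (dabigatran or SOC), for the purpose of this contact only. The text on switching from dabigatran to SOC can stay as it is.
2. In the option allowing a single late contact, state that in either arm the contact also asks for dated recurrent VTE and dated bleeding, unless the family has agreed to vital status only. Dates are needed because recurrences after Day 84 + 7 do not count in the primary analysis.

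The SAP rule need not change for this point. The cost is a few more questions in a contact that is already planned. No visit, image, blood sample or treatment rule changes, and families who withdraw consent are unaffected.
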